6.1.4 Assessment of Compliance with Study Procedural Intervention

Not applicable

7 Study Procedures and Schedule

7.1 Study Procedures/Evaluations

7.1.1 Study Specific Procedures

- Bronchoalveolar lavage from regions of the primary tumor and from the distal portion of the same lung on day 0
- BCI on day 0
- Blood draws on day 0 (prior to BCI) and on days 7 and 14 (± 3 days) (post-BCI)

7.1.2 Standard of Care Study Procedures

Pre-BCI screening:

- Medical history (including cancer and cancer treatment history, co-morbidities, functional status, and social history)
- Medication and treatment history (specifically if patient is on a platelet inhibitor other than aspirin
 or anticoagulant), and if patient has previously or is currently receiving chemotherapy, radiation
 therapy, or immunotherapy.
- Physical examination (vital and full physical exam will be performed by clinical team prior to determining patient's fitness for undergoing bronchoscopy
- Chest CT assessment to evaluate for the presence of a bronchus or airway path leading directly to the peripheral lung tumor
- Screening laboratory evaluation as described in Section 7.2
- Pre-BCI blood collection for immune analysis

During bronchoscopy:

• Bronchoalveolar lavage (BAL) will be performed in two locations, which are the regions of the primary tumor and of the distal portion of the same lung. BAL is a standard of care component of routine bronchoscopy for lung cancer.

CONFIDENTIAL

- If there is no pre-existing biopsy-proven non-small cell lung cancer diagnosis, on-site pathology review of a tissue biopsy obtained during bronchoscopy may be performed, if technically feasible or if the patient does not have high risk features for possible non-small cell lung cancer (see above).
- After the standard-of-care portion of the bronchoscopy is complete, the peripheral tumor will need to be identified by radial EBUS. If the peripheral tumor cannot be identified within 20 minutes, then BCI will not be performed.
- BCI will be performed in eligible candidates

Post-BCI:

- Monitor for any adverse events from day 0 to day 7 Post-BCI blood collection for immune analysis on day 7 ± 3
- Post-BCI blood collection for immune analysis on day 14 ± 3
- Patients who undergo BCI and are found not to have non-small cell lung cancer will be monitored for adverse events from day 0 to day 7 and be followed up at a standard of care pose-bronchoscopy visit within 7 ± 3 days. These patients will not have post-BCI blood collected.

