Reports of hemoptysis after percutaneous cryoablation have been small volume and self-limited in the majority of cases (10, 11). For example, in a review of 117 consecutive patients treated with 193 cryoablation sessions of lung tumors, there were no episodes of life-threatening pulmonary hemorrhage (11). However, there have been rare case reports of life-threatening pulmonary hemorrhage previously(12). Post- percutaneous cryoablation hemoptysis may be due to tumor necrosis from freezing or due to lung injury from the cryoprobe traversing through lung parenchyma. In percutaneous cryoablation, cryoprobes with diameters up to 3mm have been used to safely administer freeze times lasting up to 20 minutes 7, 10). In BCI, a smaller cryoprobes of 1.1mm or 1.9mm will administer significantly shorter freeze times based on a dose escalation protocol (see figure). Based on the tolerability of percutaneous cryoablation with non-significant bleeding (if bleeding occurs), significant hemoptysis is not anticipated to occur in BCI. Additionally, the shorter freeze phases, smaller diameter (1.9mm) of the cryoprobe, and avoiding the need for the cryoprobe to traverse through lung parenchyma will further decrease the risk of bleeding in BCI compared to percutaneous cryoablation.

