5.6 Duration of Study Participation

The total duration of study participation is 14 days. BCI will be performed at time of standard of care bronchoscopy on day 0. Peripheral blood will be collected by the investigatory team prior to BCI on the day of procedure, which will be drawn off the intravenous catheter inserted for the standard of care bronchoscopy to avoid a separate blood draw whenever possible. The investigatory team will also collect blood samples at approximately 7 days and 14 days after BCI (± 3 days). During each blood

draw, the volume of blood collected will be approximately 2 teaspoons (10 ml). This will occur at routine standard of care follow up clinic visits whenever possible. Alternatively, the investigatory team will collect blood samples at approximately 7 days and 14 days after BCI at the Perlmutter Cancer Center.

Total Number of Participants and Sites

- Total number of participants: 15-24
- Sites: New York University Langone Medical Center

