7.3.3.2 Visit 2: Day 14 (± 3) post-BCI

- Vital signs and physical exam
- Record adverse events as reported by participant or observed by investigator
- Collect blood for immune analysis

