7.3.4 Data Collection

Data on patients' pathologic diagnosis, cancer surveillance imaging results, demographics, smoking history, cancer history, and medical history will be collected by researchers. Tumor sizes on any available cancer surveillance imaging, cancer treatment history, and mortality data will also be collected for up to one-year post-bronchoscopic cryo-immunotherapy by researchers.

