8.2.4 Time Period and Frequency for Event Assessment

The occurrence of an AE or SAE may come to the attention of study personnel during study visits and interviews of a study participant presenting for medical care, or upon review by a study monitor. All AEs including local and systemic reactions not meeting the criteria for SAEs will be captured on the appropriate RF. Information to be collected includes event description, time of onset, clinician's assessment of severity, relationship to study product (assessed only by those with the training and authority to make a diagnosis), and time of resolution/stabilization of the event. All AEs occurring while on study must be documented appropriately regardless of relationship. All AEs will be followed to adequate resolution.

Any medical condition that is present at the time that the participant is screened will be considered as baseline and not reported as an AE. However, if the study participant's condition deteriorates at any time during the study, it will be recorded as an AE. UPs will be recorded in the data collection system throughout the study.

Changes in the severity of an AE will be documented to allow an assessment of the duration of the event at each level of severity to be performed. AEs characterized as intermittent require documentation of onset and duration of each episode.

The PI will record all reportable events with start dates occurring any time after informed consent is obtained until 7 (for non-serious AEs) or 30 days (for SAEs) after the last day of study participation. At each study visit, the investigator will inquire about the occurrence of AE/SAEs since the last visit. Events will be followed for outcome information until resolution or stabilization.

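### Adverse-event collection ends at day 7 in one section and at about day 21 or 44 in another, so the pooled AE tables mix unequal observation times

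*Combined protocol and SAP*

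**What the plan says.** - **7.1.2 (Post-BCI):** "Monitor for any adverse events from day 0 to day 7". This is not limited to DLTs.
- **7.1.2, treated participants without NSCLC:** those "found not to have non-small cell lung cancer will be monitored for adverse events from day 0 to day 7", with one standard-of-care visit at 7 ± 3 days. It adds: "These patients will not have post-BCI blood collected". No day 14 contact is described for them.
- **5.7.2:** a participant who withdraws after BCI is telephoned about AEs for the seven days after the procedure.
- **7.3.3.2 (day 14 ± 3):** "Record adverse events as reported by participant or observed by investigator".
- **8.2.4:** events are recorded from consent "until 7 (for non-serious AEs) or 30 days (for SAEs) after the last day of study participation".
- **5.6:** "The total duration of study participation is 14 days".
- **10.3 and 10.4.3:** everyone treated is analysed. AEs are reported in total and by dose level, each counted once per participant, and no time window is given.
- **8.4:** the study is suspended after a set number of grade 3 related AEs and terminated for certain events. Neither rule has a time limit.
- **3.1, 4.2.1 and 8.1:** the DLT window is seven days for everyone.
- **7.3.4:** data are gathered after the visits end, and "mortality data will also be collected for up to one-year post-bronchoscopic cryo-immunotherapy by researchers".

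**The concern.** Safety is a primary endpoint. Because 10.4.3 counts an event once per participant, each AE result is a proportion of participants with an event, and that proportion grows with the time each person is observed. The plan fixes no such time. An event on day 10 lies outside the monitoring in 7.1.2 but inside 8.2.4, and it would be asked about at the day 14 visit.

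The gap is widest for two groups whose follow-up is assigned only to day 7: treated participants who turn out not to have NSCLC, and those who withdraw. The first group is foreseeable, because 5.1 admits patients on high-risk features when on-site pathology is not feasible or cannot confirm NSCLC. The end points in 8.2.4 run from the last day of participation, which is undefined for both groups, so their windows cannot be worked out without a guess.

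The by-dose AE profile that accompanies the MTD would therefore combine people watched for different lengths of time. It is also unclear which late events could count towards the rules in 8.4.

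**Working it through.** The plan states no figure that depends on these windows, so there is nothing to reproduce. The check is window arithmetic followed by an illustration.

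**1. End of capture for a participant with NSCLC**

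- 7.1.2: day 7.
- 7.3.3.2: day 14 ± 3, that is day 11 to 17.
- 8.2.4 with 5.6, non-serious AEs: 14 + 7 = day 21.
- 8.2.4 with 5.6, SAEs: 14 + 30 = day 44.

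**2. End of capture for a treated participant without NSCLC**

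- 7.1.2: day 7, with the only visit at 7 ± 3, that is day 4 to 10.
- 8.2.4: not defined. If day 7 is *assumed* to be the last day, non-serious AEs end at 7 + 7 = day 14 and SAEs at 7 + 30 = day 37.

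**3. Observation time compared**

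| Basis | Without NSCLC | With NSCLC | Ratio |
|---|---|---|---|
| Visit schedule | 7 days | 14 days | 0.50 |
| 8.2.4, non-serious (day 7 assumed) | 14 days | 21 days | 0.67 |
| 8.2.4, SAE (day 7 assumed) | 37 days | 44 days | 0.84 |
| 7.1.2 read alone, or a common day 0-7 window | 7 days | 7 days | 1.00 |

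On the SAE row, one participant without NSCLC in a cohort of three removes (44 − 37)/(3 × 44) = 7/132 = 5.3% of follow-up time.

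**4. Illustration on the visit schedule, the widest contrast**

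The documents give no AE rate. Assume a constant hazard and a 14-day risk r of 10%, 30% or 50%. The risk by day T is 1 − (1 − r)^(T/14). At r = 30%, the day 7 risk is 1 − 0.70^0.5 = 16.3%. For a cohort of three with m participants lacking NSCLC, the expected proportion with an AE is [(3 − m) × risk(14) + m × risk(7)]/3:

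| m | Person-days | r = 10% | r = 30% | r = 50% |
|---|---|---|---|---|
| 0 | 42 | 10.0% | 30.0% | 50.0% |
| 1 | 35 | 8.4% | 25.4% | 43.1% |
| 2 | 28 | 6.8% | 20.9% | 36.2% |
| 3 | 21 | 5.1% | 16.3% | 29.3% |

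Toxicity is identical down each column; only the cohort mix changes. For one participant with NSCLC at r = 30%, the section followed moves the expected proportion from 16.3% (day 7) to 30.0% (day 14) to 41.4% (day 21).

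**5. What does not move**

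Escalation (6.1.2) and the MTD (10.4.3) depend only on DLTs, which have the same seven-day window for everyone, including participants without NSCLC and those who withdraw.

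**The case against.** The strongest reply is that 8.2.4 is the governing section on event periods. On that view the day 14 visit is an assessment point inside its window, and 7.1.2 describes active monitoring matched to the DLT window. The day 14 part of this is fair: the direct conflict is between 7.1.2 and 8.2.4. But 7.1.2 refers to any adverse event, and 8.2.4 still does not say when participation ends for those without NSCLC or those who withdraw.

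Part of the late period is also covered. Section 8.2.4 has participants told at the last visit to report later related events, requires unresolved events to be followed, and has later related deaths and AEs notified to the sponsor. Section 7.3.4 collects mortality. These help, but they do not define a common window for the tables.

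The AE tables are descriptive, so no test or error rate changes. Early clustering of events, plausible after a single procedure on day 0, would shrink the distortion. Both points stand and limit the size.

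The documents do not support three stronger readings that a reader might draw:

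- **That the MTD rests on uneven follow-up.** It does not; the DLT window is fixed.
- **That late toxicity is under-counted at longer freeze times.** No window varies by dose. The background remark that "percutaneous cryoablation hemoptysis may be due to tumor necrosis from freezing" concerns the percutaneous procedure, gives no timing, and is offered alongside probe injury as another cause.
- **That SAE follow-up is 44 days for some and 7 for others.** This applies 8.2.4 to one group and withholds it from the other, and 8.2.4 makes no such exclusion.

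**Conclusion.** The point holds as an inconsistency in current text that reaches a primary safety output. Sections 7.1.2 and 8.2.4 give different ends to AE collection, two groups of treated participants have no defined end under 8.2.4, and 10.3 with 10.4.3 pool everyone without a common cut-off.

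The inequality is 7 v 14 days on the visit schedule, or 14 v 21 days (non-serious) and 37 v 44 days (SAE) under 8.2.4. The last two pairs rest on taking day 7 as the last day for participants without NSCLC. The AE proportions in the working also rest on an assumed rate and a constant hazard, and show only that cohort mix alone could roughly halve an observed AE proportion in the extreme case.

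Dose levels differ in observation time only if participants without NSCLC or withdrawn participants are unevenly spread, which can easily happen by chance with three to six per level. The rules in 8.4 rely on the same AE capture, so the set of late events that could count towards them is also unsettled. The DLT window, dose escalation and MTD are not affected.

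**What to change.** 1. Reconcile 7.1.2, 7.3.3.2 and 8.2.4 to one AE period and one SAE period, each counted in days from BCI. Apply them to every treated participant, including those without NSCLC, and to withdrawn participants where consent permits (5.7.2). This removes the dependence on an undefined last day of participation. Make clear how the AE capture used in 8.4 relates to these periods.
2. In 10.4.3, report AEs by dose level for days 0-7, the window assigned to everyone. List later events separately, with the number of participants followed.
3. Add SAE fields to the data collection already planned in 7.3.4.

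The cost is amendment wording, slightly more data abstraction and one split table, with no extra visits or participants. One limit remains: non-serious AEs after day 7 may stay incomplete where no contact is scheduled, which is why later events should be listed with the number followed and not merged into the by-dose proportions. The DLT window needs no change on this account.

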7.2 Laboratory Procedures/Evaluations

7.2.1 Clinical Laboratory Evaluations

Screening Laboratory Evaluation:

- **Hematology:** hemoglobin, hematocrit, white blood cells (WBC) with differential count, platelet count.
- **Biochemistry:** basic metabolic panel
- **Coagulation Panel:** INR, PTT (only if deemed necessary by the proceduralist as part of standard of care pre-bronchoscopy clinical assessment)
- **Pregnancy test:** In pre-menopausal women (women who have had a menstrual period within the past twelve months), a pregnancy test is to be done within 24 hours prior to study intervention and results must be available prior to administration of study procedure.

Study Laboratory Evaluation:

- **Pre-BCI blood collection:** Two lavender top blood tubes (approximately 10cc) will be collected for analysis of peripheral blood mononuclear cells and serum
- **Bronchoalveolar lavage:** Collected from regions of the primary tumor and of the distal portion of the same lung
- **Post-BCI day 7 blood collection:** Two lavender top blood tubes (approximately 10cc) will be collected for analysis of peripheral blood mononuclear cells and serum
- **Post-BCI day 14 blood collection:** Two lavender top blood tubes (approximately 10cc) will be collected for analysis of peripheral blood mononuclear cells and serum

For further details, pre- and post-BCI peripheral blood immune analysis is described in detail in Section 4.1.2 (Secondary Study Endpoints: Immune Analysis).

7.2.2 Other Assays or Procedures

None

CONFIDENTIAL

7.2.3 Specimen Preparation, Handling, and Storage

Peripheral blood will be collected by the investigatory team prior to BCI on the day of procedure, which will be drawn off the intravenous catheter inserted for the standard of care bronchoscopy to avoid a separate blood draw whenever possible. This will occur in pre-op area, bronchoscopy suite, or operating room. Bronchoalveolar fluid will be collected during the bronchoscopy. The investigatory team will also collect blood samples at approximately 7 days and 14 days after BCI. This will occur at routine standard of care follow up clinic visits whenever possible. Alternatively, the investigatory team will collect blood samples at approximately 7 days and 14 days after BCI at the Perlmutter Cancer Center.

The investigators will store bronchoalveolar lavage fluid and blood samples on ice, and transport samples to the [name] Environmental Lung Disease Laboratory at NYU/Bellevue Medical Center or the [name] Translational Lung Biology Laboratory at NYU Medical Center. The investigators will then process specimens. After isolated peripheral mononuclear cells undergo FACS, if additional processing is not to occur immediately, samples will be stored in a -80C freezer in the locked [name] Environmental Lung Disease Laboratory at NYU/Bellevue Medical Center or the [name] Translational Lung Disease Laboratory at NYU/Bellevue Medical Center or the [name] Translational Lung Disease Laboratory at NYU/Bellevue Medical Center or the [name] Translational Lung Disease Laboratory at NYU/Bellevue Medical Center or the [name] Translational Lung Biology Laboratory at NYU Medical Center.

7.2.4 Specimen Shipment

Not applicable

7.3 Study Schedule

7.3.1 Screening

Screening Visit (Day -28 to 0)

- Review medical history, medications, and chest CT scan.
- Determine eligibility based on inclusion/exclusion criteria.
- Obtain informed consent of potential participant verified by signature on written informed consent form.
- Collect screening labs (if not already collected by clinical team): basic metabolic panel, complete blood count, and coagulation panel (if deemed necessary by the proceduralist).
- Schedule study visits for participants for day 7 and day 14 post-BCI (will attempt to coincide with scheduled office visit if possible).

7.3.2 Enrollment

Enrollment (Day -28 to Day 0)

- Obtain informed consent of potential participant (if not collected above) verified by signature on study informed consent form.
- Verify inclusion/exclusion criteria.
- Obtain urine pregnancy test (if applicable).
- Confirm demographic information, medical history, medication history, alcohol and tobacco use history.
- Record vital signs, results of examinations, other assessments.
- Collect pre-BCI peripheral blood sample
- Perform bronchoalveolar lavage during standard-of-care bronchoscopy
- Perform BCI

CONFIDENTIAL

7.3.3 Study Visits

7.3.3.1 Visit 1: Day 7 (± 3) post-BCI

- Vital signs and physical exam
- Record adverse events as reported by participant or observed by investigator
- Collect blood for immune analysis

7.3.3.2 Visit 2: Day 14 (± 3) post-BCI

- Vital signs and physical exam
- Record adverse events as reported by participant or observed by investigator
- Collect blood for immune analysis

7.3.4 Data Collection

Data on patients' pathologic diagnosis, cancer surveillance imaging results, demographics, smoking history, cancer history, and medical history will be collected by researchers. Tumor sizes on any available cancer surveillance imaging, cancer treatment history, and mortality data will also be collected for up to one-year post-bronchoscopic cryo-immunotherapy by researchers.

7.3.5 Withdrawal/Early Termination Visit

If the subject withdraws or if early termination occurs, the participant will not be asked to provide further blood specimens.

7.3.6 Unscheduled Visit

Unscheduled visits will not occur. In the event of an adverse event requiring medical attention, the participant will be directed to seek immediate attention from their clinical team or to the emergency department.

7.4 Concomitant Medications, Treatments, and Procedures

All concomitant prescription medications taken during study participation will be recorded on the case report forms (CRFs). For this protocol, a prescription medication is defined as a medication that can be prescribed only by a properly authorized/licensed clinician. Medications to be reported in the CRF are concomitant prescription medications, over-the-counter medications and non-prescription medications.

In treatment naïve patients undergoing a diagnostic bronchoscopy, enrollment in this study will not lead to a delay in appropriate, standard of care treatment. Involvement in this study is not anticipated to preclude enrollment in any other ongoing clinical trial. In patients undergoing a diagnostic or therapeutic bronchoscopy who are already receiving treatment with chemotherapy, radiation, or immunotherapy, combination therapy with BCI could theoretically affect anti-tumor immune responses.

7.5 Justification for Sensitive Procedures

Not applicable

7.5.1 Precautionary Medications, Treatments, and Procedures

Not applicable

7.6 Prohibited Medications, Treatments, and Procedures

Patients currently on a platelet inhibitor (such as clopidogrel) other than aspirin or NSAIDs, or on a blood thinner (such as heparin, enoxaparin, or a novel oral anticoagulant) may be at increased risk for bleeding during their standard of care bronchoscopy or due to BCI. These medications will need to be held prior to planned bronchoscopy at the discretion of the proceduralist. If prohibited medications are not discontinued, then the patient will not be a candidate for BCI.

7.7 Prophylactic Medications, Treatments, and Procedures

None

7.8 Rescue Medications, Treatments, and Procedures

In the event of dose-limiting toxicity, rescue medication, treatments, and procedures may be necessary.

- Grade 2 bleeding may be treated with iced saline, topical epinephrine, or placement of an endobronchial blocker
- Grade 3 bleeding may require bronchial artery embolization or surgical intervention
- Pneumothorax may require chest tube placement based on size and other clinical features

7.9 Participant Access to Study Agent at Study Closure

BCI will only be performed once at time of standard of care bronchoscopy.

8 Assessment of Safety

8.1 Specification of Safety Parameters

Dose-limiting toxicities (DLT) will be used to guide the dose-escalation procedure and determine the maximum tolerated dose. A DLT is defined as any of the following occurring up to 7 days post-BCI:

- Grade 2 or 3 bleeding, based on the following scale (34):
 - a) Grade 0: absence of bleeding
 - b) Grade 1: bleeding requiring suctioning to clear
 - c) Grade 2: bleeding requiring an endoscopic procedure (iced saline, 1:20,000 topical epinephrine, or bronchial occlusion)
 - d) Grade 3: severe bleeding (>100cc total volume). Severe bleeding will also be defined as bleeding which cannot be controlled endoscopically, requires ICU admission or interventional radiology/ surgical intervention, or results in respiratory or hemodynamic instability (34)
- pneumothorax necessitating tube thoracostomy; recorded features of pneumothorax to include:
 - a) size
 - b) associated symptomatology
 - c) respiratory impairment
 - d) need for chest tube placement
- any NCI CTCAE (33) Grade 3, 4, or 5 adverse events, which may be possibly, probably, or definitely related to BCI

